10.5 Interim analyses

No interim efficacy analysis is planned. However, safety and toxicity analysis will be conducted on an ongoing basis by the Winship Cancer Institute DSMC.

10.6 Sample size and power considerations

The sample size of up to 30 patients is required to establish the MTD and the RP2D based on the proposed modified Fibonacci dose escalation schema assuming that each dose cohort requires the maximum of 6 subjects. Up to 6 subjects will be enrolled at each dose level. If no DLTs occur, a total of 15 subjects will be needed to complete the dose escalation part of the study. To further characterize safety and efficacy, fifteen additional subjects will be enrolled at the MTD in an expansion cohort. In order to perform preliminary evaluation of anti-tumor activity, the sample size at the MTD or highest dose level cohort is determined by a power analysis. It is assumed that the subjects would have no response if they would not have received any therapy and that response rate for subjects in the MTD or highest dose level cohort would be 10%. Based on this assumption, a sample size of 15 subjects in the MTD cohort will provide more than 79% power in a one-sample exact binomial test at the significance level of 0.05. We anticipate accrual of 2-3 patients per month for the escalation phase and approximately 1-2 patients per month for the expansion phase, which is restricted to patients with clear cell renal cell carcinoma. At this accrual rate, we expect total accrual and study completion within 18-24 months.

A parallel expansion cohort of 9 patients with adenoidcystic carcinoma will also be evaluated. An objective response in at least 3 of 9 patients will be considered sufficient evidence to explore the benefit of this regimen in a larger phase II efficacy trial. The expected maximum overall sample size of 45 patients will still be maintained with the addition of this parallel cohort because only 21 of the maximum expected 30 patients were required in the dose escalation of the study.

11 Regulatory Considerations

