5.1 Overall design

This is a phase I, open-label, single institution, non-randomized study of escalating doses of daily, orally administered lenalidomide in combination with standard doses of everolimus, an orally available mTOR inhibitor. The trial is open to patients with advanced solid malignancies who have failed or are intolerant of available standard treatment options for their disease. Dose escalation will proceed in a modified Fibonacci 3+3 fashion with the requirement that dose escalation to the next level can only proceed if 0 of 3 or ≤ 1 of 6 patients experience a dose limiting toxicity (DLT). Four escalating dose cohorts and three deescalating dose cohorts will be used to evaluate different doses of lenalidomide and everolimus starting with the approved and or clinically relevant doses of both agents. The proposed starting dose level 1 is 10mg of lenalidomide (days 1 – 28) in combination with 10mg of everolimus (days 1 - 28) in a 28-day cycle. A serial de-escalation to 10mg of lenalidomide (days 1-21 of a 28 day cycle) and 5mg of everolimus will be carried out if DLT is observed in $\geq 33\%$ of patients enrolled to the starting dose cohort. The MTD is the highest dose level of lenalidomide and everolimus (up to a maximum dose of 25mg and 10mg respectively) at which $<33\%$ of the dose cohort experiences DLT after 1 cycle (28 days) of therapy. The established MTD will be the recommended dose for follow-up phase II study. To obtain preliminary clinical benefit of this combination, an expanded cohort of 15 patients with clear cell renal cell carcinoma, adenoidcystic carcinoma and neuroendocrine tumors will be treated at the define MTD. To allow for assessment of drug-drug interaction using PK analysis, lenalidomide will be administered alone on day 1 of the first cycle followed by both agents on day 2 cycle 1. Both drugs will be started simultaneously on day 1 of all subsequent cycles.

In addition, a parallel cohort of 9 additional patients with adenoicystic cancer will be treated at the RP2D. This is to enable us to obtain further evidence in support of the efficacy of this regimen in patients with adenoicystic cancer as observed in the limited number of patients with this cancer type who were enrolled in the escalation phase of the study.

Table 1

Dose Level	Lenalidomide (day 1 to 28)	Everolimus (day 1-28)	Patient Enrolment	Remarks
-2	10mg Days 1-21	5mg every other day	3 + 3	If DLT, study will close without defining a MTD

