-1	10mg Days 1-21	5mg	3 + 3	Deescalate to level -2 if ≥ 1 of 6 patients experience DLT, otherwise declare as MTD and expand the cohort
Starting Dose 1	10mg	5mg	3 + 3	Escalate to level 2 if 0 of 3 or 1 of 6 patients experience DLT, otherwise deescalate 1 level
2	15mg	5mg	3 + 3	Escalate to level 3 if 0 of 3 or 1 of 6 patients experience DLT, otherwise deescalate 1 level
3	20mg	5mg	3 + 3	Escalate to level 4 if 0 of 3 or 1 of 6 patients experience DLT, otherwise deescalate 1 level
4	25mg	5mg	3 + 3	if ≥ 1 of 6 patients experience deescalate 1 level, otherwise declare as MTD
5	25mg	10	3 + 3	if ≥ 1 of 6 patients experience deescalate 1 level, otherwise declare as MTD
MTD	TBD	TBD	15	Expanded cohort of 15 patients restricted to patients with renal cell carcinoma, adenoicystic carcinoma and neuroendocrine tumors

5.1.1 Blood Sample Collection:

Blood samples will be collected in heparinized green top tubes (3 mls for PK samples and 7 mls for PBMC collection), red top tube (7 mls to obtain serum sample for cytokine assay). PBMC will be purified using standard Ficoll-Paque gradient centrifugation according to the instructions of the manufacturer (Amersham Pharmacia, Uppsala, Sweden). All samples must be stored away within 1 hour of collection by refrigeration at -80°C until ready for assay.

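### The MTD and RP2D rest on at most 6 escalation patients, and the plan does not say how DLTs in the 24 expansion patients bear on them or set a numeric DLT boundary for expansion

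*Combined protocol and SAP*

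**What the plan says.** Section 10.6 ties both dose outcomes to escalation: "The sample size of up to 30 patients is required to establish the MTD and the RP2D". It caps each cohort ("Up to 6 subjects will be enrolled at each dose level") and adds that "If no DLTs occur, a total of 15 subjects will be needed to complete the dose escalation part of the study", which is 3 per level over 5 levels.

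Section 5.1 defines the MTD as the highest level at which fewer than 33% of the dose cohort have a DLT in cycle 1. It also fixes the next step: "The established MTD will be the recommended dose for follow-up phase II study".

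The 5.1 text says "dose escalation to the next level can only proceed if 0 of 3 or" no more than 1 of 6 have a DLT. The Table 1 rows for levels 4 and 5 read differently. There, if 1 or more of 6 "patients experience deescalate 1 level, otherwise declare as MTD".

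Expansion follows: "To further characterize safety and efficacy, fifteen additional subjects will be enrolled at the MTD in an expansion cohort", and 9 more with adenoid cystic carcinoma are treated at the RP2D. Section 5.7.1 sends cohort dose decisions to Table 1, whose MTD row gives a patient number and tumour types but no DLT rule.

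On oversight, section 10.5 says "safety and toxicity analysis will be conducted on an ongoing basis" by the institutional DSMC. Section 9.3 adds investigator review of toxicities, weekly Phase I toxicity meetings, IRB notification if risk/benefit changes, protocol amendments, and a DMC that may stop the study. Section 11.5 allows discontinuation for medical reasons. Section 10.4 summarises adverse events by dose level and lists DLTs individually.

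**The concern.** The MTD/RP2D is the first primary objective, and its criterion is a DLT proportion. The plan applies that criterion explicitly only while the cohort is 3 to 6 patients, when the proportion is least well known. With 6 escalation patients, 24 of the 30 treated at the chosen dose (80%) come afterwards. They carry most of the information on the DLT rate, but no analysis compares their DLTs with the 33% limit.

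If DLTs run high in expansion, the plan leaves three things open: whether they change the MTD, how many would matter, and which rate is reported with the recommended dose. These would then be settled after the data are seen, on a primary endpoint.

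**Working it through.** **Plan's own figures.** Escalation maximum 5 x 6 = 30; minimum 5 x 3 = 15; total 30 + 15 = 45, and after the added cohort 21 + 15 + 9 = 45. Power for 15 patients at a 10% response rate, needing at least one response: 1 - 0.9^15 = 79.4%. All agree with section 10.6. The issue is not an arithmetic error.

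**Precision at the decision** (exact Clopper-Pearson 95% intervals):
- 0/6: 0-45.9%
- 1/6: 0.4-64.1%
- 5/30, the same observed 16.7% after pooling 6 + 24: 5.6-34.7%

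**Chance that a single level passes.** The true DLT rate p is assumed; the documents give none. Under 0/3 or 1/6 the probability is (1-p)^3 + 3p(1-p)^5. If 0/6 is needed, it is (1-p)^6.
- p = 33%: 0.301 + 0.134 = 43%; with 0/6, 9.0%
- p = 40%: 0.216 + 0.093 = 31%; with 0/6, 4.7%
- p = 50%: 0.125 + 0.047 = 17%; with 0/6, 1.6%

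These apply to one level. They are not the probability that such a dose ends up as the MTD.

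**Would expansion reveal the problem?** At p = 40%, 24 x 0.40 = 9.6 DLTs are expected, and P(at least 8 of 24, i.e. 33% or more) = 81%. At p = 50%, 12 are expected and the probability is 97%. The signal would usually be there; a stated use for it is missing.

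**A pooled check at the protocol's own limit.** Look after each 6 expansion patients, pooled with 6 escalation patients, and refer for review at 4/12, 6/18, 8/24 or 10/30 (each 33.3%). The exact probability that review is triggered at any look is:

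| Assumed true DLT rate | Starting from 1/6 | Starting from 0/6 |
|---|---|---|
| 17% | 9% | 2% |
| 20% | 15% | 4% |
| 25% | 29% | 11% |
| 30% | 46% | 24% |
| 40% | 79% | 60% |
| 50% | 96% | 88% |

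**The case against.** A reader might infer that nothing in the plan lets expansion DLTs prompt a review, so that a too-toxic dose necessarily remains the RP2D. The documents do not support that. Sections 9.3, 10.5 and 11.5 provide continuing review, IRB notification, amendments and power to stop. Carrying a too-toxic dose forward is a risk, not a certainty.

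A reader might also infer that the 24 patients contribute nothing to the primary endpoint. That is wrong too: safety is itself a primary objective and endpoint, and section 10.4 covers everyone treated. Nor does the plan exclude pooling. The synopsis defines the MTD by DLTs in the treated cohort, and section 4.2.1 sets the cycle-1 DLT assessment without restricting it to escalation.

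Two further points stand. The 31% and 43% pass rates depend on the 0/3 or 1/6 rule and fall sharply if levels 4 and 5 need 0/6. The pooled check also has a real cost at true rates of 25-30%, below the 33% limit, where it often calls a review; section 10.6 expects only 1-2 expansion patients a month. The look schedule is a reviewer's choice.

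What the objection does not answer is that none of the review routes has a numeric boundary or says whether expansion DLTs count in the MTD/RP2D. The DMC's stated stopping power is linked to interim analyses, while section 10.5 plans none for efficacy and gives no schedule for the safety analysis.

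**Conclusion.** The gap is real but limited: oversight exists, while the rule linking expansion DLTs to the MTD/RP2D does not. As written, a dose at or above 33% DLT in expansion could still be recommended, subject to unscripted judgement.

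The chance that a level with a true 40% rate passes escalation is 31% or 4.7%, depending on which rule governs. Section 5.1 and Table 1 must be reconciled on this. Under either starting count, a pooled check would flag such a dose more often than not (79% from 1/6, 60% from 0/6).

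The conclusion rests on assumed true DLT rates, on 6 evaluable escalation patients at the chosen dose, and on all 24 expansion patients being treated at that dose and evaluable in cycle 1. This is a cheap improvement that should be made; no figure in the plan is wrong.

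**What to change.** Add a paragraph to sections 10.5 and 10.6:

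1. Cycle-1 DLTs in all expansion patients are assessed with the existing criteria and pooled with escalation patients treated at the same dose.
2. The pooled DLT rate is reported with an exact 95% confidence interval alongside the MTD.
3. After about every 6 expansion patients, a pooled rate at or above the protocol's 33% limit is referred to the existing DSMC for a documented review of the MTD/RP2D. Whether accrual is held is left to the DSMC.

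Separately, reconcile the escalation rule in the 5.1 text with the Table 1 rows for levels 4 and 5.

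The cost is drafting time and some unneeded reviews: 9-15% at true rates of 17-20% and 29-46% at 25-30% when starting from 1/6 (2-4% and 11-24% from 0/6). DLT criteria, the cycle-1 window and the DSMC are already in place, so no new data are needed.

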11.1 Institutional Review Board/Ethics Committee approval

The protocol for this study has been designed in accordance with the general ethical principles outlined in the Declaration of Helsinki. The review of this protocol by the IRB/EC and the performance of all aspects of the study, including the methods used for obtaining informed consent, must also be in accordance with principles enunciated in the declaration, as well as ICH Guidelines, Title 21 of the Code of Federal Regulations (CFR), Part 50 Protection of Human Subjects and Part 56 Institutional Review Boards.

The Investigator will be responsible for preparing documents for submission to the relevant IRB/EC and obtaining written approval for this study. The approval will be obtained prior to the initiation of the study.

The approval for both the protocol and informed consent must specify the date of approval, protocol number and version, or amendment number.

Any amendments to the protocol after receipt of IRB/EC approval must be submitted by the Investigator to the IRB/EC for approval. The Investigator is also responsible for notifying the IRB/EC of any serious deviations from the protocol, or anything else that may involve added risk to subjects.

Any advertisements used to recruit subjects for the study must be reviewed and approved by the IRB/EC prior to use.

11.2 Informed consent

The Investigator must obtain informed consent of a subject or his/her designee prior to any study related procedures as per GCPs as set forth in the CFR and ICH guidelines.

Documentation that informed consent occurred prior to the subject's entry into the study and the informed consent process should be recorded in the subject's source documents. The original consent form signed and dated by the subject and by the person consenting the subject prior to the subject's entry into the study, must be maintained in the Investigator's study files.

11.3 Subject confidentiality

Celgene affirms the subject's right to protection against invasion of privacy. In compliance with United States federal regulations, Celgene requires the Investigator to permit representatives of Celgene Corporation and, when necessary, representatives of the FDA or other regulatory authorities to review and/or copy any medical records relevant to the study in accordance with local laws.

Should direct access to medical records require a waiver or authorization separate from the subject's statement of informed consent, it is the responsibility of the Investigator to obtain such permission in writing from the appropriate individual.

11.4 Study records requirements

The Investigator must ensure that the records and documents pertaining to the conduct of the study and the distribution of the protocol therapy, that is copies of CRFs and source documents (original documents, data, and records [e.g., hospital records; clinical and office charts; laboratory notes; memoranda; subject's diaries or evaluation checklists; SAE reports, pharmacy dispensing records; recorded data from automated instruments; copies or transcriptions certified after verification as being accurate copies; microfiches; photographic negatives, microfilm, or magnetic media; x-rays; subject files; and records kept at the pharmacy, at the laboratories, and at medico-technical departments involved in the clinical study; documents regarding subject treatment and drug accountability; original signed informed consents, etc.]) be retained by the Investigator for as long as needed to comply with national and international regulations (generally 2 years after discontinuing clinical development or after the last marketing approval). The Investigator agrees to adhere to the document/records retention procedures by signing the protocol.

13.1 Appendix A – ECOG Performance Status Scale

SCORE	DESCRIPTION
0	Fully active, able to carry on all pre-disease performance without restriction.
1	Restricted in physically strenuous activity but ambulatory and able to carry out work of a light or sedentary nature, e.g., light house work, office work.
2	Ambulatory and capable of all self-care but unable to carry out any work activities. Up and about more than 50% of waking hours.
3	Capable of only limited self-care, confined to bed or chair more than 50% of waking hours.
4	Completely disabled. Cannot carry on any self-care. Totally confined to bed or chair.
5	Dead.

13.2 Appendix B: Risks of Fetal Exposure, Pregnancy Testing Guidelines and Acceptable Birth Control Methods

Risks Associated with Pregnancy

The use of lenalidomide in pregnant females and nursing mothers has not been studied nor has the effect of the lenalidomide on human eggs and sperm. The risks to a fetus are not known. However, because lenalidomide is related to thalidomide, and thalidomide is known to cause severe birth defects, the following requirements must be observed.

All study participants must be registered into the mandatory RevAssist® program, and be willing and able to comply with the requirements of RevAssist®.

Females of childbearing potential (FCBP)[†] must agree to use two reliable forms of contraception simultaneously or to practice complete abstinence from heterosexual intercourse during the following time periods related to this study: 1) for at least 28 days before starting lenalidomide; 2) while participating in the study; and 3) for at least 28 days after discontinuation from the study. The two methods of reliable contraception must include one highly effective method (i.e. intrauterine device (IUD), hormonal [birth control pills, injections, or implants], tubal ligation, partner's vasectomy) and one additional effective (barrier) method (i.e. latex condom, diaphragm, cervical cap). FCBP must be referred to a qualified provider of contraceptive methods if needed.

Because of the increased risk of venous thromboembolism in patients with multiple myeloma taking lenalidomide and dexamethasone, combined oral contraceptive pills are not recommended with regimens combining lenalidomide and dexamethasone. If a patient is currently using combined oral contraception the patient should switch to one of the other highly effective methods listed above. The risk of venous thromboembolism continues for 4–6 weeks after discontinuing combined oral contraception. The efficacy of contraceptive steroids may be reduced during co-treatment with dexamethasone.

Before starting lenalidomide:

Female Subjects:

- FCBP must have two negative pregnancy tests (sensitivity of at least 50 mIU/mL) prior to prescribing lenalidomide. The first pregnancy test must be performed within 10-14 days

[†] A female of childbearing potential is a sexually mature woman who: 1) has not undergone a hysterectomy or bilateral oophorectomy; or 2) has not been naturally postmenopausal for at least 24 consecutive months (i.e., has had menses at any time in the preceding 24 consecutive months).

prior to prescribing lenalidomide and the second pregnancy test must be performed within 24 hours prior to prescribing lenalidomide (prescriptions must be filled within 7 days). The subject may not receive lenalidomide until the Investigator has verified that the results of these pregnancy tests are negative.

Male Subjects:

- Must agree to use a latex condom during sexual contact with females of childbearing potential while participating in the study and for at least 28 days following discontinuation from the study even if he has undergone a successful vasectomy.

During study participation and for 28 days following discontinuation from the study:

All Subjects:

- If pregnancy or a positive pregnancy test does occur in a study subject or the partner of a male study subject during study participation, lenalidomide must be immediately discontinued.

Female Subjects:

- FCBP with regular or no menstrual cycles must agree to have pregnancy tests weekly for the first 28 days of study participation and then every 28 days while on study, at study discontinuation, and at day 28 following discontinuation from the study. If menstrual cycles are irregular, the pregnancy testing must occur weekly for the first 28 days and then every 14 days while on study, at study discontinuation, and at days 14 and 28 following discontinuation from the study.
- In addition to the required pregnancy testing, the Investigator must confirm with FCBP that she is continuing to use two reliable methods of birth control at each visit.
- Pregnancy testing and counseling must be performed if a subject misses her period or if her pregnancy test or her menstrual bleeding is abnormal. Lenalidomide treatment must be discontinued during this evaluation.

Male Subjects:

- Must agree to use a latex condom during sexual contact with females of childbearing potential while participating in the study and for at least 28 days following discontinuation from the study even if he has undergone a successful vasectomy.

